8.2.4. Efficacy analysis

Efficacy will be evaluated using all data collected during the observation period without classifying the data into Vyndaqel and Vynmac unless otherwise specified.

8.2.4.1. NYHA functional classification

The NYHA functional classification at each evaluation time point [at baseline, Month 12, Month 30, discontinuation] will be summarized as described in Section 8.1.2.

The NYHA functional classification at each evaluation time point after the start of treatment [at Month 12, Month 30, discontinuation] will be summarized using a cross table as described in Section 8.1.2.

8.2.4.2. Cardiac biomarkers

For NT-pro BNP, BNP, troponin I, and troponin T each, the following analyses will be performed:

Measurements of each biomarker at each evaluation time point [at baseline, Month 6, Month 12, Month 18, Month 24, Month 30, discontinuation] will be summarized as described in Section 8.1.1. In addition, a

change from baseline in each biomarker at each evaluation time point [at Month 12, Month 30, discontinuation] will be summarized as described in Section 8.1.1.

A change from baseline in each biomarker at each evaluation time point will be summarized, as described in Section 8.1.5, using an MMRM with patient as a random effect; TTR genetic variant [wild-type, variant], NYHA functional classification [I/II, III/IV], and evaluation time point [Month 6, Month 12, Month 18, Month 24, Month 30] as fixed effects; and baseline value as a covariate. The analysis will be performed on values measured on the nearest day to each time point for the evaluation using the model.

Evaluation time points may be changed depending on the status of data accumulation.

In addition, measured values at all time points in each patient will be used to prepare spaghetti plots for the entire observation period, as described in Section 8.1.5. (Figures using different colors [or separated by line type] will be prepared for both TTR genetic variant [wild-type, variant] and NYHA functional classification [I, II, III, IV].)

Preparation of an MMRM and figures will not be included in the subgroup analysis.

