### 8.3.1. Patient characteristics

1. Enter the information at the start of administration of this drug into the registration form.

- a. Site information (if the study is conducted using paper CRFs)
- b. ID number
- c. Gender
- d. First day of treatment with this drug for ATTR-CM (first administration day of a marketed product of this drug for patients transferred from clinical trials, hereinafter the same)
- e. Identification of transferred patients (in the case of transferred patients, enter the patient registration number of the original site)
- f. Usage experience of this drug [administered this drug for the first time, transferred from clinical trials, or in treatment for transthyretin-type familial amyloid polyneuropathy (TTR-FAP) but also started to receive the treatment of ATTR-CM] (no entry is necessary for transferred patients)

If the patient is a transferred patient and the patient registration number of the original site has been entered, the entries for the following items g. to i. are not necessary (the entries are necessary even for the transferred patient if the patient registration number of the original site is not clear)

- g. Birth year (known at the start of administration of this drug) (if the birth year cannot be disclosed, enter the age at the start of administration of this drug)
  - h. Disease type of ATTR-CM (wild-type, variant, or unknown)
  - i. Severity of heart failure (NYHA Functional Classification)
2. The following will be recorded in CRF at the start of administration of this drug. If the contents of the registration form have been reflected, the investigator will check the contents again and make corrections as necessary.
- a. ID number
  - b. Gender

- c. Identification of transferred patients (in the case of transferred patients, enter the patient registration number of the original site)
- d. Usage experience of this drug (administered this drug for the first time, transferred from clinical trials, or in treatment for TTR-FAP but also started to receive the treatment of ATTR-CM) (no entry is necessary for transferred patients)

If the patient is a transferred patient and the patient registration number of the original site has been identified, the entries for the following items e. to o. are not necessary (the entries are necessary even for the transferred patient if the patient registration number is not clear)

- e. Birth year/age
- f. Inpatient/outpatient status
- g. Height (cm)
- h. Body weight (kg)

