8.1.5. Analysis of longitudinal data measured repeatedly

When longitudinal data is analyzed using a mixed model repeated measure (MMRM), parameters will be estimated using the restricted maximum likelihood estimation method (REML), and an unstructured variance-covariance structure will be assumed for within-subject variation. If the model fails to converge, a different available optimization method will be tried. If the problem of convergence is still not resolved, estimation will be performed by changing the assumption of variance-covariance structure in the order of TOEPH, ARH(1), AR(1), and CS. The model-adjusted mean change from baseline at each evaluation time point will be summarized using the least squares mean and its 95% confidence interval.

When individual data are graphically presented, the time-courses of all measured values will be presented using line graphs.

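### The biomarker MMRM is over-parameterised as written and leaves the unknown TTR category, the least squares mean weighting and the analysis scale unspecified

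*SAP*

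**What the plan says.** **The model.** SAP 8.2.4.2 fits each of NT-proBNP, BNP, troponin I and troponin T "using an MMRM with patient as a random effect". TTR type enters with two levels (wild-type or variant), as does NYHA class (I/II against III/IV). The rest of the fixed part reads "evaluation time point [Month 6, Month 12, Month 18, Month 24, Month 30] as fixed effects; and baseline value as a covariate". Change is the response, introduced as "A change from baseline in each biomarker at each evaluation time point will be summarized, as described in Section 8.1.5". No transformation is named in either document.

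**The estimation rules.** SAP 8.1.5 calls for REML estimation. For the covariance it says that "an unstructured variance-covariance structure will be assumed for within-subject variation". On non-convergence, another optimiser is tried first. Should that not help, the next step is "changing the assumption of variance-covariance structure in the order of TOEPH, ARH(1), AR(1), and CS". Results are "summarized using the least squares mean and its 95% confidence interval", with no statement of how factor levels are weighted.

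**The TTR categories.** Protocol 8.3.1 collects "Disease type of ATTR-CM (wild-type, variant, or unknown", and SAP 8.2.2.1 tabulates all three categories. The model factor has two. SAP 8.2.3.3 excludes unknown data from the safety risk ratios, but no rule covers the biomarker model.

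**What stands beside the model.** SAP 8.2.4.2 also plans unmodelled summaries with mean and median (SAP 8.1.1): values at every visit, and change at Month 12, Month 30 and discontinuation. Spaghetti plots are planned too. SAP section 4 treats any test as exploratory.

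**The concern.** An unstructured matrix already describes every variance and covariance among a patient's five visits, so a patient variance on top of it has nothing left to estimate. The practical risk lies in the SAP's own convergence rule: a redundant term could cause the failure that moves the analysis to a more restrictive covariance. The SAP does not say whether a singular-fit warning counts as non-convergence, so two programmers could take different paths.

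The other gaps affect what the reported mean refers to. A single-arm survey is meant to describe its own patients, so it matters whether the adjusted mean reflects their TTR and NYHA mix, whether patients of unknown TTR type are in it, and whether it is a raw difference or a ratio.

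These choices carry weight because the MMRM is the only specified source of biomarker change at Months 6, 18 and 24, and of any interval for biomarker change. Protocol section 5 planned database release for November 2024 and SAP version 6.0 is dated 23 January 2025, so anything left open may be settled with data in hand.

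**Working it through.** The documents give no figure for the biomarker model, so there is none to reproduce here. Their only probability is the unrelated one in Protocol 8.5.2 (at least 10 cases among 300 at 5.88%, stated as about 98%); the exact binomial gives 0.984, which agrees.

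**1. Counting covariance parameters.** Inputs from the SAP: 5 visits, unstructured covariance, one patient variance.

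- Estimable quantities: 5 × 6 / 2 = 15.
- Parameters: 15 + 1 = 16.

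The implied covariance is V = s²·J + R, with s² the patient variance, J a matrix of ones and R the within-patient structure. The numerical rank of the derivative of V with respect to its parameters is:

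| R, plus patient effect | Parameters | Rank |
|---|---|---|
| Unstructured | 16 | 15 |
| TOEPH | 10 | 10 |
| ARH(1) | 7 | 7 |
| AR(1) | 3 | 3 |
| CS | 3 | 2 |

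The first choice and the last fallback are not identifiable. The three between them are, at least locally.

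**2. Effect on the estimates if the fit converges.** One V was split four ways (s² = 0, 0.160, 0.320, 0.575) on simulated data with 300 patients. Each split gave the same REML value (−1498.086729), Month 30 coefficient (1.337814) and standard error (0.224302). Only the split is undetermined. This evaluates a fixed V and is not a full maximisation.

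**3. Weighting: precision.** Suppose equal weights and a variant share w (not in the documents). Relative to the cohort-weighted mean,

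SE ratio = 0.5 × √(1/w + 1/(1−w)).

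- w = 0.05: 2.29
- w = 0.10: 0.5 × √(10 + 1.111) = 1.67
- w = 0.20: 1.25

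**4. Weighting: shift.** With both factors, variant share p, NYHA III/IV share q, and the two factors assumed independent,

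shift = (0.5 − p)·b(TTR) + (0.5 − q)·b(NYHA),

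SE ratio = √(1 + (0.5−p)²/[p(1−p)] + (0.5−q)²/[q(1−q)]).

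For p = 0.1, q = 0.2 the ratio is √(1 + 1.778 + 0.5625) = 1.83. For N = 300 at one visit, with both effects b in residual SD units:

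| p, q (assumed) | SE ratio | Shift, b = 0.2 | Coverage of cohort mean, b = 0.2 | Shift, b = 0.5 | Coverage of cohort mean, b = 0.5 |
|---|---|---|---|---|---|
| 0.1, 0.2 | 1.83 | 0.14 | 73.6% | 0.35 | 8.7% |
| 0.2, 0.3 | 1.32 | 0.10 | 74.2% | 0.25 | 9.5% |
| 0.3, 0.4 | 1.11 | 0.06 | 84.5% | 0.15 | 35.2% |
| 0.5, 0.5 | 1.00 | 0 | 95.0% | 0 | 95.0% |

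With b = 0 the shift is 0 and coverage is 95% in every row.

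**5. Scale.** The documents give no biomarker distribution. The illustration assumes a log-normal baseline and a multiplicative change (log mean 0.1, log SD 0.5) at one visit. Coverage of the nominal 95% interval for mean raw change:

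| Baseline log-SD (assumed) | n = 300 unadjusted / baseline-adjusted | n = 100 unadjusted / baseline-adjusted | Mean change ÷ baseline median | Median change ÷ baseline median |
|---|---|---|---|---|
| 0.6 | 94.5% / 93.8% | 92.9% / 92.0% | 0.30 | 0.09 |
| 0.9 | 93.3% / 91.9% | 91.6% / 89.4% | 0.38 | 0.07 |
| 1.2 | 92.2% / 89.5% | 88.6% / 84.1% | 0.52 | 0.06 |

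The adjusted standard error conditions on the observed baselines, so part of its shortfall is not due to skewness.

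**The case against.** The strongest reply is that little in the results need change. Step 2 shows that the redundant variance leaves means and intervals untouched when the fit converges. The wording may simply be loose for patient as the subject of the repeated measures. The analysis is exploratory, no significance level is set, the main objective is long-term safety, and observed means and medians are reported on the cohort's own mix. All of this stands, and it lowers the consequence. It does not supply an interval, or a change at Months 6, 18 and 24, from anywhere but the model.

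A reader might also infer that the fallback would end at CS and impose one variance on all visits. The SAP does not support that. Other optimisers come first, then TOEPH and ARH(1), which allow a different variance at each visit and are identifiable with the patient effect. The redundant term gives no reason to go as far as CS.

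Equal weighting and right skew are not in the documents either. The first is a common software default and the second an assumption about positive concentrations. Raw mean change is a legitimate quantity, and the loss of coverage in step 5 is moderate at n = 300. What remains on both points is an omission: the SAP does not state its choice.

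**Conclusion.** The point holds as a correction to the specification, with moderate confidence. Read literally, the model has 16 covariance parameters for 15 estimable quantities, and 3 for 2 under CS. The harm is conditional: none if the fit converges, an avoidable change of covariance structure if it does not. Patients of unknown TTR type have no stated place in the model; their number is not given.

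The size of the weighting gap rests on assumptions. Equal weights would make the means refer to a 50:50 TTR and NYHA mix. At an assumed 10% variant share the standard error is about 1.67 times the cohort-weighted one (1.25 at 20%, 2.29 at 5%), and the mean shifts by 0.40 times the variant minus wild-type difference from TTR alone. The shift is zero if the TTR and NYHA effects are zero.

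It would be tempting to conclude that the model's estimates do not describe the cohort. The documents do not support that, because the weighting is unstated, the mix and effects are unknown, and unmodelled summaries of the cohort are reported alongside.

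**What to change.** In SAP 8.2.4.2:

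- Delete the phrase making patient a random effect. Name patient as the subject and keep the unstructured covariance of 8.1.5, which then has 15 parameters for 15 quantities.
- In 8.1.5, say whether a singular-fit warning counts as non-convergence.
- Request least squares means with observed margins, taken over patients and not over records.
- Add unknown as a third level of the TTR factor.
- Analyse the log ratio to baseline with log baseline as covariate, and report geometric mean ratios with 95% confidence intervals beside the raw summaries already planned. If the raw scale is preferred, say so and why.

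The cost is a few lines of SAP text and a few program options, with no new data. The small downside is that ratios are less familiar than raw differences. A log scale also needs a rule for any value reported as zero or below a detection limit.

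### As written, the biomarker MMRM is over-parameterised and has no time interactions; this can trigger needless covariance fallback and, under differential dropout, may bias the Month 30 mean

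*SAP*

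**What the plan says.** SAP 8.2.4.2 summarises change from baseline in NT-proBNP, BNP, troponin I and troponin T "using an MMRM with patient as a random effect". TTR type and NYHA (I/II against III/IV) enter as fixed effects, together with "evaluation time point [Month 6, Month 12, Month 18, Month 24, Month 30] as fixed effects; and baseline value as a covariate". No interaction is listed. The section refers to SAP 8.1.5 for the method.

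SAP 8.1.5 uses REML and states that "an unstructured variance-covariance structure will be assumed for within-subject variation". On failure the steps are:

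- "If the model fails to converge, a different available optimization method will be tried".
- If that does not help, estimation proceeds by "changing the assumption of variance-covariance structure in the order of TOEPH, ARH(1), AR(1), and CS". Dropping the random effect is not among the steps.

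The reported result is also set there: "The model-adjusted mean change from baseline at each evaluation time point will be summarized using the least squares mean and its 95% confidence interval".

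Three other provisions bear on the point:

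- Protocol 8.2.6 ends observation at the first visit after the drug is stopped.
- SAP section 7 leaves missing biomarker values unimputed.
- SAP section 4 calls the study non-confirmatory and treats p-values as descriptive.

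**The concern.** There are two separate issues.

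**Covariance.** An unstructured matrix already contains any variance shared across a patient's visits. A random patient intercept on top of it cannot be estimated separately. Software may then report a singular Hessian or non-convergence that has nothing to do with the data. Another optimiser cannot cure non-identification, so a program that follows the text may give up the unstructured model for a problem created by the specification.

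**Mean model.** With main effects only, both NYHA groups, both TTR types and all baseline levels are forced onto parallel courses over 30 months. Patients who stop treatment soon leave observation, and the model fills in their later course from that parallel assumption. If the groups diverge and the faster-progressing group leaves sooner, the overall Month 30 mean leans on the early group difference and understates late progression. In a single-arm study no control contrast can cancel such an error.

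**Working it through.** **Plan's own figure.** The documents give no figure for the biomarker model: no retention, variance, correlation or effect size. Their only design probability is about 98% for at least 10 hepatotoxicity cases among 300 at 5.88% (Protocol 8.5.2). It reproduces as 0.984 by the binomial tail, but has no bearing here.

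**Step 1: identification.** Write the marginal covariance of the five visits as V = R + σ_b²J, where J is the 5×5 matrix of ones. Count the parameters and take the rank of the derivative of V with respect to them.

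| R | Parameters in R | With random intercept | Rank |
|---|---|---|---|
| Unstructured | 5×6/2 = 15 | 16 | 15 |
| TOEPH | 9 | 10 | 10 |
| ARH(1) | 6 | 7 | 7 |
| AR(1) | 2 | 3 | 3 |
| CS | 2 | 3 | 2 |

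The starting model and the last fallback are redundant; the three structures between them are not. In one simulated data set, every σ_b² tried from 0 to 0.30 gave the same V and the same REML likelihood.

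**Step 2: does the redundancy move the means?** No. V and the fixed effects stay identified. In simulations with 60,000 patients, the unstructured model with and without the random intercept gave the same likelihood and the same Month 30 mean to three decimals in every scenario.

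**Step 3: what would a fallback do?** TOEPH and ARH(1) keep a separate variance for each visit. With additive truth and dropout at random (about 62% observed at Month 30), Month 30 bias on an outcome with SD about 1.2 was +0.006 unstructured, +0.005 TOEPH, +0.005 ARH(1), −0.029 AR(1) and −0.034 CS. Simulation noise is about 0.01.

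AR(1) and CS impose a common variance. Assume that retention falls linearly from 100% at Month 6 to 60% at Month 30 and that variance rises linearly. The retention-weighted pooled variance is then 1.4375 (Month 6 = 1) if the Month 30 variance is 2, and 2.3125 if it is 4.

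- SE ratio: √(1.4375/2) = 0.85 and √(2.3125/4) = 0.76.
- Coverage, 2Φ(1.96 × ratio) − 1: 90% and 86%.

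**Step 4: omitted interactions.** This uses the large-sample generalised least squares expectation of the main-effects model. All inputs are assumed: NYHA III/IV 25%; progression linear in time; monotone dropout, linear from 100% at Month 6 to the stated Month 30 retention; correlation 0.7, either exchangeable or AR(1); means weighted by the population NYHA mix.

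- *III/IV progresses three times as fast* (Month 30 change 0.3 against 0.1). True mean 0.75×0.1 + 0.25×0.3 = 0.150. With retention 40% against 80%, the model gives 0.137 (−9%) exchangeable and 0.140 (−6%) AR(1).
- *Only III/IV progresses* (0.4 against 0). True mean 0.25×0.4 = 0.100. With retention 30% against 80%, it gives 0.066 (−34%) exchangeable and 0.075 (−25%) AR(1).
- *First case with equal retention:* 0.150 against 0.150, no bias.

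**Step 5: simulation at n = 300.** Dropout is at random, with about 40% missing at Month 30. NYHA III/IV is 35%, variant 20%, and residual variance rises over visits.

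| Truth | Model | Month 30 bias | 95% CI coverage |
|---|---|---|---|
| Interaction 0.4 | SAP fixed effects, unstructured | −0.060 | 89% |
| Interaction 0.4 | SAP fixed effects, CS | −0.105 | 59% |
| Interaction 0.4 | Time interactions added, unstructured | −0.004 | 97% |
| Additive | SAP fixed effects, unstructured | −0.001 | 94% |
| Additive | SAP fixed effects, CS | −0.038 | 83% |

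The Monte Carlo SE of the bias is 0.005 to 0.006.

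**The case against.** **The random-effect phrase may only name the repeated-measures subject.** SAP 8.1.5 describes a single covariance, for within-subject variation. On that reading the identification issue disappears. This stands as a possibility. The two readings are different programs, so the SAP should say which is meant.

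**A reader might infer that the redundancy biases the means.** It does not (step 2).

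**A reader might infer that the model will slide to AR(1) or CS.** The text does not make that likely. AR(1) is reached only after the unstructured fit, a second optimiser, TOEPH and ARH(1) have all failed, and the redundancy explains only the first two failures. The coverage losses in step 3 are therefore remote.

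**A reader might infer that Month 30 is biased, or that faster progression in sicker patients is hidden.** Bias needs both a covariate-by-time effect and dropout related to those covariates or to earlier values. The documents give no figures for either, and the SAP does not state how the least squares means are weighted. Divergence would not go unseen: SAP 8.2.4.4 and 5.4 apply the descriptive biomarker summaries by TTR type and NYHA, and 8.2.4.2 plans spaghetti plots distinguished by both. Only the MMRM and figures are left out of the subgroup analysis.

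**Consequence and cost.** The main objective is long-term safety, and no decision rule rests on this model. The 300 patients are the safety set. Biomarkers come from routine records and baseline must fall within 30 days before the first dose, so numbers per marker may be well below 300 and extra terms may strain the fit. All of this stands and limits the weight of the point.

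**Conclusion.** The point holds in conditional form. Taken literally, the covariance is not identified (16 parameters for 15 quantities, and 3 for 2 under CS). The harm is a possible false trigger of the fallback, not biased means. TOEPH and ARH(1) would do little damage; only AR(1) or CS would distort visit-specific intervals.

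The missing time interactions matter more. Differential dropout is plausible because observation ends soon after discontinuation. Under the assumed inputs in step 4, Month 30 progression is understated by about 6–9% in the milder case and about 25–34% in the extreme one, and by nothing with equal retention. These sizes rest on assumed retention, progression and correlation, and on population-weighted means. The analysis is exploratory, so this is a worthwhile low-cost correction and not a threat to the study's main conclusions.

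**What to change.** - **SAP 8.2.4.2, covariance:** replace the random-effect phrase with *patient as the subject of the repeated (unstructured) covariance*.
- **SAP 8.2.4.2, mean model:** add baseline-by-time and NYHA-by-time interactions, and TTR-by-time only if the number of variant patients allows.
- **SAP 8.1.5, optional:** use robust (sandwich) standard errors if AR(1) or CS is reached. These repair the intervals, not the bias.

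The cost is SAP wording and program syntax, plus 5 − 1 = 4 extra parameters for each interaction. In the additive-truth simulation at n = 300, adding all three interactions raised the average Month 30 model SE from 0.081 to 0.084. The loss will be larger for a biomarker measured in far fewer patients, so check the numbers per marker before the terms are fixed.

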5.4. Subgroups

Subgroup analyses of safety will be performed for the following patient characteristics and other factors. For the patient characteristics and other factors with those of specific categories underlined, a risk ratio will be calculated using each underlined category as the reference.

- Inpatient/outpatient status at the first prescription [inpatient, outpatient]
- *Severity of liver impairment [absent, mild, moderate, severe]
- Liver impairment [absent, present]
- Renal impairment [absent, present]
- Age [<15 years, ≥15 to <65 years, ≥65 years]
- *TTR genetic variant [wild-type, variant]
- NYHA functional classification [Class I/II, III/IV]
- NYHA functional classification [Class I, II, III, IV]
- Concomitant medication [absent, present]
- Non-drug therapy (device therapy) [absent, present]

- Complication [absent, present]
- Gender [male, female]
- Usage experience of this drug (administered this drug for the first time, transferred from clinical trials, transition from the treatment of ATTR-PN)

*Evaluation of the important missing information (safety in patients with severe liver impairment and patients with variants)

Subgroup analyses of efficacy will be performed for the following patient characteristics:

- TTR genetic variant [wild-type, variant]
- NYHA functional classification [Class I/II, III/IV]
- NYHA functional classification [Class I, II, III, IV]

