8.2.4.4. Exploratory analysis

For each of the factors specified in Section 5.4, subgroup analyses will be performed for the efficacy analyses described in Section 8.2.4. Kaplan-Meier estimation will be used to analyze the survival time by using the factors shown in Section 5.4 as stratification variables.

Additional analyses may be performed as necessary. The exploratory analysis will be reported only when results giving important interpretation are obtained.

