11. APPENDICES

11.1. Appendix 1: Details of Data Extraction

A1.1 Definition of Efficacy Evaluation Time Points

Visit time	Endpoints	Definition [Time window]
At baseline	Laboratory tests, efficacy endpoints	Between 30 days before the first date of administration (start date of administration) and the start date of administration in this study. For NYHA functional classification, the evaluated value of NYHA functional classification entered in the "Target disease" page of the case report form will be adopted.
Month 6	Laboratory tests, efficacy endpoints	Between 3 months and 9 months after the start of administration
Month 12	Laboratory tests, efficacy endpoints	Between 9 months and 15 months after the start of administration
Month 18	Laboratory tests, efficacy endpoints	Between 15 months and 21 months after the start of administration
Month 24	Laboratory tests, efficacy endpoints	Between 21 months and 27 months after the start of administration
Month 30	Laboratory tests, efficacy endpoints	Between 27 months and 39 months after the start of administration
At discontinuation	Laboratory tests, efficacy endpoints	1 month before or after the last date of administration in this study

If there are multiple values of the same endpoint at the same visit time, the value measured on the closest day to each visit time will be adopted. If there are multiple values measured on the closest day, the value measured at a later date will be adopted.

11.2. Appendix 2: Example of Risk Ratios of Subgroups to the Incidence of Adverse Reactions

Non-English text

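### Biomarker and NYHA changes pool inpatient and outpatient starters, so recovery from an admission could look like effectiveness; show them by status as well

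*SAP*

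**What the plan says.** Protocol 8.3.1 has the investigator record, at the start of administration, "f. Inpatient/outpatient status". It does not ask why an inpatient was admitted. SAP 5.4 makes "Inpatient/outpatient status at the first prescription [inpatient, outpatient" the first of its safety subgroup factors. The same section then has a separate list, opened by "Subgroup analyses of efficacy will be performed for the following patient characteristics", which holds only TTR type and two groupings of NYHA class. SAP 8.2.2.1 tabulates inpatient/outpatient status for the efficacy analysis set, but as a characteristic only.

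For NYHA class, SAP 8.2.4.1 says that post-baseline values "will be summarized using a cross table as described in Section 8.1.2", that is, against baseline class and without adjustment. For the biomarkers, SAP 8.2.4.2 plans summary statistics for the change, plus a repeated-measures model with fixed effects "TTR genetic variant [wild-type, variant], NYHA functional classification [I/II, III/IV], and evaluation time point" and the baseline value as covariate. It adds: "Preparation of an MMRM and figures will not be included in the subgroup analysis".

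The biomarker baseline in SAP Appendix 1 (A1.1) comes from the 30 days up to and including the first dose. Where several values exist, "the value measured on the closest day to each visit time will be adopted". Baseline NYHA class is the one entered in the case report form for the start of treatment.

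**The concern.** In a single-arm study, a baseline that is temporarily bad produces later improvement whatever the drug does. A patient who starts the drug in hospital may have a biomarker value or NYHA class recorded during the admission. If the admission was for worse heart failure, both would tend to improve afterwards. Pooled with stable outpatients, that recovery would be read as effectiveness, or would hide a true worsening. The plan already treats status at first prescription as worth separating for safety, but not for the two effectiveness outcomes that depend on the baseline.

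What is at stake is interpretation. No hypothesis is tested at a set level (SAP 4 and 4.1). However, the approval conditions quoted in Protocol 7 ask for effectiveness data as well as safety data, and the final analysis serves the reexamination application (SAP 3).

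**Working it through.** **The plan's own figure.** There is none on this point. The one computed probability, about 98% in Protocol 8.5.2, concerns safety. The exact binomial P(X ≥ 10) with n = 300 and p = 0.0588 is 0.984, so it reproduces, but it plays no part here.

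**Inputs.** From the documents: no control group (Protocol 8.9), target of 300 patients (Protocol 8.5.1), and the analyses described above. Not in the documents, and therefore assumed:
- f, the inpatient share of starters
- a, the fraction of those admitted for worse heart failure
- r, the ratio of their baseline to their usual level
- q, the fraction of inpatient starters whose NYHA class later improves by recovery alone

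The true drug effect is set to zero, and inpatients and outpatients are given the same usual mean level.

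**Biomarkers, untransformed.** The plan specifies arithmetic summaries and no log transformation, so the calculation stays on that scale. With the usual mean set to 1, the pooled baseline is 1 + fa(r − 1) and the later mean is 1. The false change as a share of baseline is

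−fa(r − 1) / [1 + fa(r − 1)].

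| f | a | r | false change |
|---|---|---|---|
| any | 0 | any | 0% |
| 5% | 1 | 1.25 | −0.0125/1.0125 = −1.2% |
| 10% | 1 | 1.5 | −0.05/1.05 = −4.8% |
| 20% | 0.5 | 2 | −0.10/1.10 = −9.1% |
| 20% | 1 | 2 | −0.20/1.20 = −16.7% |
| 30% | 1 | 2 | −0.30/1.30 = −23.1% |

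**NYHA.** The false improvement among all patients is f × q:
- 5% × 30% = 1.5 percentage points
- 20% × 50% = 10 points
- 30% × 70% = 21 points
- zero if q = 0

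SAP 8.1.2 uses each baseline class as denominator, so the effect would fall in the rows where inpatient starters sit.

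**Does the planned adjustment remove it?** Take f = 20%, a = 1, r = 2, with no other variation. Outpatients have baseline 1 and change 0; inpatients have baseline 2 and change −1. The regression of change on baseline is change = 1 − baseline. Evaluated at the mean baseline, 0.8 × 1 + 0.2 × 2 = 1.2, it gives −0.2, exactly the unadjusted mean change (0.8 × 0 + 0.2 × (−1) = −0.2). A main effect for status, averaged over the observed mix, gives −0.2 again. Only the estimate by status shows 0 for outpatients and −1 for inpatients.

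This is a general property of least squares with one time point and complete data: the fit at the covariate means equals the raw mean. A simulation agreed (300 patients, 300 runs, one post-baseline time point, a log-scale biomarker, no drug effect, baseline and NYHA class as covariates). At inpatient shares of 10%, 20% and 30%, the adjusted and unadjusted overall changes were the same to one decimal. Adding status averaged over the mix altered nothing, and outpatient starters alone showed about zero. I use it only to check the adjustment, since the plan has no log-scale analysis. The full model, with dropout and its own weighting over factor levels, will not match the raw mean exactly, but none of its terms identifies an admission.

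**The case against.** The strongest objection is that the premise is not in the documents. Status is recorded, the reason for admission is not, and an admission for diagnostic work-up would bring little or no recovery. This stands, and it is why the size may be near zero.

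Status is also an imperfect marker in both directions. The 30-day window lets an inpatient starter have a biomarker value from before the admission, and lets an outpatient starter have one from a recent admission. An outpatient start prompted by worsening symptoms can also be followed by regression to the mean. This stands too. A reader might infer that outpatient starters give a clean estimate of effectiveness; the documents do not support that. Preferring them would also narrow a survey meant to cover all treated patients (Protocol 8.2.5.1 and 8.7).

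A reader might want survival split by status for the same reason. Survival time is not a change from baseline, so the argument does not reach it.

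It can be said that SAP 8.2.4.4 already covers the point, because for the factors in Section 5.4 "subgroup analyses will be performed for the efficacy analyses described in Section 8.2.4". But Section 5.4 has its own efficacy list without status, and even the broad reading leaves out the model. The option of additional analyses fixes nothing in advance, and the same section reports exploratory results only when they are judged important.

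The planned NYHA subgroups and plots separate the groups in part, if admitted patients sit in the higher classes. They do not tell a recovering inpatient from a stable outpatient of the same class.

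Finally, the study is non-confirmatory and aimed mainly at safety. That limits the weight of the point but does not answer it. The limitations in Protocol 8.9 name the missing control group only for adverse events, and put confounding down to insufficient background information; here the item is collected.

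**Conclusion.** The point holds as a cheap improvement. The biomarker and NYHA changes pool inpatient and outpatient starters. Any recovery from an admission would appear as effectiveness, and the planned baseline and NYHA covariates would not take it out of the overall mean change.

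The size cannot be fixed from the documents. Under the assumed ranges it runs from zero to a false fall of 23.1% in the untransformed biomarker mean, and from zero to 21 percentage points of false NYHA improvement. Every value above zero depends on the assumed inpatient share and on some admissions being for worse heart failure. A reader might infer that the planned results are invalid or that an observed improvement is an artefact. The documents do not support that: they show only that the planned tables could not tell the two apart.

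**What to change.** Add "Inpatient/outpatient status at the first prescription [inpatient, outpatient"] to the efficacy subgroup list in SAP 5.4, for the NYHA cross tables of 8.2.4.1 and the biomarker change summaries of 8.2.4.2. Present these by status beside the all-patient result, and keep the all-patient result as the main one. Do not make outpatient starters the preferred population.

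If status also enters the repeated-measures model, include its interaction with evaluation time point and report least squares means by status, as a sensitivity analysis. A main effect alone leaves the overall mean change as it was. State in the report that status is a proxy and that the reason for admission was not recorded.

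The cost is SAP wording and a few tables from an item already collected, with less precise estimates within strata. If all 300 patients were evaluable and 10% started as inpatients (30 patients), then with equal variance the interval for inpatients would be about √(300/30) = 3.2 times as wide as the pooled one. For the 270 outpatients it would be about √(300/270) = 1.05 times as wide. Database release was planned for November 2024 (Protocol 5) and SAP version 6.0 is dated January 2025. If that release date held, the added analyses should be labelled as specified after release.
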